Overview of study approach. In a 24 week RCT based in a large urban area with high rates of OUD and HIV, we will recruit 250 out-of-treatment opioid users from SEPs and randomize 1:1 to onsite BMT initiation (**O-BMT**) or enhanced referral. Over two weeks, participants in the O-BMT arm will see a buprenorphine provider twice, receive prescriptions of medication, and then their care will be transferred to a community health center (CHC) for maintenance BMT. In the control arm, participants will receive enhanced referral to a CHC for initiation and maintenance BMT. We will assess participants with urine drug tests, questionnaires, and medical record review studying treatment engagement, treatment outcomes (opioid use, HIV risk behaviors) and programmatic service utilization in order to establish effectiveness and costs. We will also assess buprenorphine diversion using electronic monitors, urine drug testing, and sequential surveys.

Setting. A. New York Harm Reduction Educators (NYRHE) is the largest harm reduction agency in New York City with over 35 staff members and serving over 5000 clients annually. At two community-based offices and 11 street-side locations, NYHRE provides participants with syringe exchange; referral for medical, dental and addiction treatment; and other supportive services. The majority of NYHRE's clients are Hispanic or black, male, 40-49 years old, and PWID. Diverse staff members (case managers, outreach workers, and syringe exchange staff) have received training on BMT. O-BMT will be offered at community-based offices only.

B. Washington Heights CORNER Project (WHCP) is another harm reduction agency situated in an area highly affected by OUD and HIV. At its community-based office, WHCP provides clients with syringe exchange; referrals for medical, dental, or addiction treatment; and other supportive services. WHCP serves over 1500 clients annually with similar characteristics as NYHRE. WHCP staff members have received training on BMT.

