Recruitment. Staff members at the SEPs will receive training on BMT (buprenorphine education and referral to the CHC).¹⁴ Active recruitment will occur by staff members discussing BMT with participants and contacting a research assistant (RA). Passive recruitment will occur by posting study flyers at study sites and asking study participants to recommend other acquaintances for the study.

Screening procedures: The RAs will screen all participants for exclusion and inclusion criteria. A diagnosis of opioid use disorder and exclusions (unstable mental illness, alcohol use disorder, benzodiazepine use disorder) will be established by applying the Mini International Neuropsychiatric Interview (MINI), a widely used psychiatric structured diagnostic interview instrument for unstable mental illness and Post Traumatic Stress Disorder and the DSM-V checklist for opioid, alcohol and benzodiazepine use disorder. For this assessment (for both alcohol and benzodiazepines), there are 11 questions asked, if the participant answers with a Yes to 2-3 of these questions, their use severity will be assessed as Mild, if they score a 4 or 5, their severity use will be assessed as moderate if they score 6 or greater, their severity will be considered Severe. Interest in BMT and motivation for treatment will be established with previously published measures.^{12,73} In addition, the PCL-5, PTSD Checklist for DSM-5 and the Life Events Checklist for DSM-5 will be conducted. Women of childbearing age will be screened with a urine pregnancy test.

Randomization: An RA will meet with eligible participants at the SEPs to describe the study. At enrollment, written informed consent including a consent quiz to monitor comprehension will be obtained, including a release for medical records. Randomization will be stratified by site (A, B or C, occur in blocks of 4-8, with 1:1 allocation of O-BMT vs. referral).

Participant tracking: To facilitate tracking participants over the 24 week follow-up period, we will use procedures that we developed to retain people who use drugs in our previous research studies, in which we have had an 84% retention rate over 6-month follow-up.⁷⁴ Locator Forms will list information about: 1) participants' address and phone number; 2) contact information of participants' family members, friends, case managers, physician, pharmacy, and drug treatment program; and 3) locations where participants hang out.

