Participants will receive an expedited appointment within 1 week of the referral and a reminder phone call the day before their appointment. If participants do not attend their first appointment at the CHC, enhanced referral procedures will be repeated as long as the request occurs within two weeks of study enrollment (in parallel with the timing of O-BMT). We will assess fidelity to these referral procedures (see below). Buprenorphine providers at the CHC will follow the same procedures for BMT initiation as provided in O-BMT: assessment for OUD and co-morbidities, instruction on starting treatment at home, weekly electronic medical adherence monitors for two weeks with 4-16 mg of buprenorphine, dose adjustment after one week, and then monthly visits. Providers at the CHC will receive instruction on study procedures before commencing the trial, and procedures will be reviewed at monthly buprenorphine provider meetings at the CHC (see Letters of Support).

Training the SEP staff. Referral to addiction treatment and psychosocial support are standard services provided by the SEPs. Prior to enrolling participants, we will enhance services by providing 3 hours of training

Principal Investigator: [name]

on BMT eligibility and procedures for making appointments and reminder phone calls. We have provided these trainings to SEP staff and peer mentors with good acceptability and fidelity to procedures.¹⁴

Methods common to all aims. We will assess for BMT engagement (at 30 days), treatment outcomes (illicit opioid use and treatment retention), HIV risk behaviors, buprenorphine diversion, programmatic costs and service utilization, and participant attitudes over the study period.

Research Visits: An RA will meet with all participants at enrollment and after 1, 2, 4, 6, 8, 12, and 24 weeks have elapsed. Research visits will occur in private at the SEP office or CHC and participants will receive a \$10 Clincard payment (weeks 1, 6) or a \$25 Clincard payment (weeks 0, 2, 4, 8, 12, 24) compensation. Interviews and urine samples will be collected at each study visit. Medical records will be extracted at the completion of the study.

Data sources and measures: A complete list of measures is presented in Table 2.

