Aim 1: To test the effectiveness of O-BMT. *H1: more participants randomized to O-BMT (vs. control) will be engaged in BMT at 30 days.* Our primary analysis will determine the effect of the intervention (O-BMT). We will use a chi square test comparing the proportion of participants in each study arm who have an active buprenorphine prescription 30 days after enrollment. We will also conduct a multivariable logistic regression adjusting for mental illness, polysubstance use, and addiction severity.

H2: Reductions in opioid use will be greater among participants randomized to O-BMT (vs. control) over 24 weeks. We will use generalized estimating equations to compare changes in opioid use between study arms over the 24 week study period. One model will use results from urine drug tests at 1, 2, 4, 6, 8, 12, and 24 weeks. A second model will compare the mean number of days (of the prior 30 days) with self-reported opioid use at 4, 8, 12, and 24 weeks.

H3: Reductions in HIV risk behaviors will be greater among participants randomized to O-BMT (vs. referral) over 24 weeks of follow-up. We will use generalized estimating equations to compare changes in injecting risk at 2, 12, and 24 weeks.

Aim 2: To test the safety of onsite buprenorphine treatment at syringe exchange programs.

H4: Diversion of buprenorphine will not be significantly greater among participants randomized to O-BMT (vs. control). By definition, participants who are not prescribed buprenorphine will not have an opportunity to divert their medication, but we will use an intention to treat approach to maintain randomization. The risk difference

Principal Investigator: [name]

threshold margin for non-inferiority will be 5%. We will construct Wald 95% confidence intervals (CIs) for a difference in diversion rates between the two arms and examine if the lower bound of the 95% CI is greater than the threshold margin. If potential confounding factors are unbalanced and require adjustment, we will apply logistic regression and estimate the Odds Ratio (OR) and its CI, examining if the lower bound of the OR is greater than the OR converted from the risk difference.

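### Site, the randomisation stratum, appears in no Aim 1 analysis, and the H2 and H3 models do not say how the week-0 value is used; the plan stays valid but gives up precision it could have almost free

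*Combined protocol and SAP*

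**What the plan says.** The Randomization paragraph states: "Randomization will be stratified by site (A, B or C, occur in blocks of 4-8", with 1:1 allocation.

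The Analysis section, Aim 1, then gives:

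- **H1, primary:** "We will use a chi square test comparing the proportion of participants in each study arm who have an active buprenorphine prescription 30 days".
- **H1, adjusted:** "We will also conduct a multivariable logistic regression adjusting for mental illness, polysubstance use, and addiction severity".
- **H2:** "We will use generalized estimating equations to compare changes in opioid use between study arms over the 24 week study period". For urine, "One model will use results from urine drug tests at 1, 2, 4, 6, 8, 12, and 24 weeks". A second model takes self-reported days of use at weeks 4, 8, 12 and 24.
- **H3:** "We will use generalized estimating equations to compare changes in injecting risk at 2, 12, and 24 weeks".

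Site is named in none of these. The allowance for adjusting unbalanced factors belongs to H4 only.

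Week 0 is collected. Under Research Visits, "An RA will meet with all participants at enrollment and after 1, 2, 4, 6, 8, 12, and 24 weeks have elapsed", and interviews and urine are taken each time. Table 2 marks the first column for urine testing, self-reported drug use and the HIV risk survey. No section says whether that value is a covariate, a first time point, a subtracted reference or unused.

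**The concern.** There are two separate omissions.

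**Site.** Stratified allocation balances the arms within site, so site differences add nothing to the true error of the arm comparison. A chi-square that ignores site still counts that variation in its standard error. The test is then conservative to the degree that engagement differs by site. The logistic model behaves differently: leaving site out mainly pulls the odds ratio towards 1 and does not inflate its standard error.

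**Week 0.** H2 and H3 are about reductions, and a reduction needs a reference value. At least four models fit the text: follow-up values only, raw change scores, week 0 as covariate, and week 0 as a time point. They differ in precision, and an analyst could choose among them after seeing results. An arm-by-time contrast fitted to post-baseline visits alone would also miss any effect already present at the first modelled visit. A plain follow-up contrast is unbiased for the between-arm difference on an additive scale, but it wastes information already collected.

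**Working it through.** **1. The plan's own figure.** Inputs from D.10 Power analysis: 16% versus 33%, 80% power, chi-square. Two-sided 5% is assumed, since no alpha is stated for H1.

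n per arm = [1.96·√(2·0.245·0.755) + 0.8416·√(0.16·0.84 + 0.33·0.67)]² / 0.17² = (1.192 + 0.502)² / 0.0289 = 99.3, so 100.

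The total is 200, and 200/0.80 = 250. Both stated figures reproduce.

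**2. H1: chi-square versus site-stratified CMH.** Simulation with 1:1 allocation within three equal sites, a common odds ratio, overall rates 16% and 33%, and no continuity correction. The documents give no site rates, so all of these are assumptions. The odds ratio column compares the highest with the lowest site.

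| Control rate by site | Site odds ratio | Power N=200, chi-square / CMH | Power N=250, chi-square / CMH |
|---|---|---|---|
| 16/16/16% | 1 | 80.6 / 80.6 | 88.5 / 88.6 |
| 12/16/20% | 1.8 | 81.0 / 80.9 | 88.9 / 89.1 |
| 8/16/24% | 3.6 | 81.2 / 82.5 | 88.9 / 89.8 |
| 4/14/30% | 10.3 | 82.0 / 85.2 | 89.9 / 92.1 |
| 3/10/35% | 17.4 | 83.1 / 88.1 | 90.8 / 94.0 |

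Repeat runs agree within about 0.4 point. With site shares of 50/25/25% the picture is the same: at a site odds ratio of 4, 81.2 versus 82.2 (N=200).

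Under the null at N=250, the chi-square rejects about 4.3% (8/16/24%) and 3.9% (4/14/30%) of the time. CMH rejects 4.9% and 5.0%.

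**3. H1: width of the risk-difference interval.** The unstratified variance is proportional to 0.16·0.84 + 0.33·0.67 = 0.3555. The stratified variance replaces each term by its within-site mean.

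- 8/16/24%, with O-BMT at 19/34/46% (common odds ratio 2.70): control (0.0736 + 0.1344 + 0.1824)/3 = 0.130; O-BMT (0.154 + 0.224 + 0.248)/3 = 0.209; ratio √(0.3555/0.339) = 1.02.
- 4/14/30%, with O-BMT at 11/32/56% (common odds ratio 2.94): control 0.123; O-BMT (0.098 + 0.218 + 0.246)/3 = 0.187; ratio √(0.3555/0.310) = 1.07.

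So the unstratified interval is about 2% and 7% wider. Plug-in variances at N=250 give 3% and 8%; just under one point of that is a small-sample effect.

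**4. H1: logistic model, N=250, without versus with site.**

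- 8/16/24%: OR 2.62 versus 2.75, SE 0.311 versus 0.320, ln(OR)/SE 3.10 versus 3.16.
- 4/14/30%: OR 2.60 versus 2.99, SE 0.310 versus 0.335, ln(OR)/SE 3.08 versus 3.27.

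The estimate moves and the standard error does not shrink.

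**5. H2: days of use.** Variance of the arm contrast at one visit relative to follow-up only, with r the assumed week-0 to follow-up correlation:

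| r | Raw change, 2(1−r) | Follow-up only | Week 0 as covariate, 1−r² |
|---|---|---|---|
| 0.3 | 1.40 | 1.00 | 0.91 |
| 0.5 | 1.00 | 1.00 | 0.75 |

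Without week 0 the SE is larger by 1/√0.91 = 1.05 to 1/√0.75 = 1.15. At N=200, adjustment is worth 200/0.91 = 220 to 200/0.75 = 267 participants.

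Averaged over four visits that correlate 0.6 (assumed), v = (1 + 3·0.6)/4 = 0.70. The SE ratio is then √(0.70/0.61) = 1.07 to √(0.70/0.45) = 1.25.

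**6. H2 and H3: binary GEE.** N=200, 4,000 simulated trials, independence working correlation, robust SE, visit effects. All rates and the latent correlations (0.3, then 0.5) are assumed. Power without versus with week 0:

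- Urine (95% positive at week 0, then 75% versus 63%): 90.9 versus 92.2; 81.7 versus 85.0.
- Injecting risk (40% at week 0, then 30% versus 20%): 67.5 versus 70.5; 59.9 versus 68.8.

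A repeat moved single figures by up to 1.9 points and left the pattern unchanged. The urine gain is small because nearly everyone is positive at week 0.

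**The case against.** **H1 is a preference, not a defect.** The chi-square is valid, the sample size was built on it, and its power is at least 80.6% at N=200 in every case above. The larger gains need site odds ratios of 10 or more, and the documents point to smaller differences. All referral-arm participants go to one health centre with expedited appointments, staff follow the same referral procedures, and "WHCP serves over 1500 clients annually with similar characteristics as NYHRE". All of this stands. It limits the size of the H1 point without removing it, because stratifying costs no power when sites are alike. The similarity statement also covers only two of the three sites.

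**The logistic shift is largely non-collapsibility.** This also stands: the odds ratio with site is a different, conditional quantity. The planned covariates might absorb part of any site difference, and this model is not the primary test.

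**The H2 and H3 comparison picks one reading.** The wording on change could mean change from baseline, so the 5 to 15% is the loss under follow-up-only analysis and not necessarily under the plan as meant. That is fair. But raw change scores never beat adjustment, since 2(1−r) − (1−r²) = (1−r)² ≥ 0, and below r = 0.5 they do worse than ignoring week 0. The recommended model is the better choice under either reading.

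**H2 and H3 are secondary, carry no power claim, and the rates used are assumed.** True. The figures indicate scale only.

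**Conclusion.** The point holds as an inexpensive improvement, not as an error in the primary test.

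- **H1:** the gain from stratifying is 0 to about 1 power point if sites are alike or differ modestly. It reaches 3 to 5 points at N=200 only under large site differences that the documents give no reason to expect. H1 has no baseline value of its own outcome to adjust for, because recent agonist treatment is an exclusion.
- **H2 and H3:** this is the part that matters. The model is not pinned down, and a follow-up-only analysis would give up 9 to 25% of the variance reduction available for days of use at r = 0.3 to 0.5. In the assumed scenarios it would cost roughly 3 to 9 power points for injecting risk, and less for urine.

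Site rates, site sizes, correlations and all outcome rates other than 16% and 33% are assumptions. The missing site term and the unstated role of week 0 are read directly from the text.

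**What to change.** Before any comparison by arm is seen:

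1. **H1.** Make the primary test a Cochran-Mantel-Haenszel test stratified by site, reported with a site-stratified risk difference and 95% confidence interval. Add site to the logistic covariates.
2. **H2 and H3.** Add site to each GEE model and state that the week-0 value of the same outcome enters as a covariate. Alternatively, enter week 0 as a time point with a baseline mean common to both arms.

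The cost is about one sentence per model. No new data are needed and N=250 is unchanged. The analysis becomes slightly more complex, and odds ratios for the binary outcomes become conditional on site and, in H2 and H3, on baseline. The stratified risk difference keeps the H1 result readable on its natural scale.

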D.10 Power analysis. To estimate the effect size for the O-BMT intervention, we drew from prior pilots of onsite treatment. Stancliff et al.⁴² offered BMT to SEP participants (N = 100) and 68% were engaged in BMT at 3 months (30 day engagement was not reported). Tringale et al.⁴³ offered BMT to SEP participants (N=9) over 15 days and then transferred care to treatment program. Following onsite initiation, 33% ultimately engaged in BMT. Daniels et al.⁸⁰ offered BMT at a community-based recovery center (N = 78) and 49% were transitioned to primary care site to continue treatment. For enhanced referral, we estimated rates of engagement in BMT

Principal Investigator: [name]

Table 3. Sample size calculation for hypothesized BMT engagement rates			
Enhanced referral arm	O-BMT arm		
	33%	49%	68%
	0%	40	26
	9%	80	36
	16%	200	62

Note: Sample sizes determined based on Fisher exact test when engagement rate in referral arm is 0.1%. For other tests, the sample sizes were determined based on Chi-square tests.

14%. Though this is larger than tolerable margins for non-inferiority, we will have good estimates of the frequency of diversion in the O-BMT arm, which will provide important safety data for onsite treatment.

For Aim 3, assumptions are based on differences in cost and effect, standard deviations of cost and effect, the correlation of the difference in cost and effect, desired confidence and power levels, and the maximum willingness-to-pay value.^{106,107} We estimated the power for the primary outcomes of our economic analysis (cost-per QALY and cost-per abstinent year) using the target sample size of 250 (125 per group), and a range of values for the aforementioned assumptions, based on prior economic evaluations of substance use disorder interventions. We estimate at least 90% power to be 95% confident that an intervention is acceptable at the commonly cited willingness-to-pay threshold of \$100,000 per QALY.⁹⁵

PROTECTION OF HUMAN SUBJECTS

Human subjects involvement and characteristics: We will enroll 250 participants from syringe exchange programs (SEPs) with opioid use disorder (OUD) who are interested in buprenorphine maintenance treatment (BMT) and are motivated for treatment.

Eligibility criteria include:

- 1) age \geq 18 years
- 2) opioid use disorder by DSM-V criteria
- 3) interest in BMT
- 4) motivation for OUD treatment, based on SOCRATES
- 5) willingness to accept CHC referral

Exclusion criteria include:

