- 1) receiving opioid agonist treatment in the past 30 days (confirmed by NY Prescription Drug Monitoring Program);
- 2) inability to provide informed consent
- 3) unstable mental illness (e.g., suicidality, psychosis, etc.)
- 4) severe alcohol use disorder or benzodiazepine use disorder by DSM-V criteria
- 5) hypersensitivity to buprenorphine or naloxone.
- 6) pregnancy (confirmed via urine testing)

Rationale for inclusion/exclusion criteria: Study participants will include out-of-treatment SEP participants with OUD. We will only include participants who are interested in BMT, motivated for OUD treatment, and willing to accept referral to a CHC for treatment, because our goal is to increase engagement in comprehensive BMT. Providing BMT onsite at SEPs could attract participants who are unready to stop illicit opioid use and only want buprenorphine temporarily to reduce withdrawal symptoms or because they do not have access to their illicit opioid of choice. There may be benefits to this type of symptom treatment, but our study is not designed to evaluate these benefits. We will exclude those with clinical contraindications to BMT,

from our own pilot data and several studies that referred SEP participants to MMT. Engagement after passive referral may be as low as 0%,¹⁴ while referral to MMT has resulted in 9-16% of SEP participants engaging in treatment.³⁷⁻³⁹ Therefore, we will recruit a sample of 250, which allowing for up to 20% attrition (n=200), giving us at least 80% power for the primary outcome (**BMT engagement**) in all proposed scenario.

For Aim 2, we chose the intention to treat analysis as the primary outcome. With a sample size of 250 and an expect rate of diversion of 10-25%, we will only have 80% power to declare that diversion rate in the O-BMT arm is non-inferior to the referral arm if the inferiority margin of the risk difference is 10-

Principal Investigator: [name]

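### If few referral-arm participants are prescribed buprenorphine, H4's Wald interval sets its upper limit too low: false non-inferiority of 3.3–5.7% against a nominal 2.5% at referral diversion of 0–4%

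*Combined protocol and SAP*

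**What the plan says.** The Analysis section, Aim 2 (H4), compares diversion between arms by intention to treat. It notes that people without a prescription have nothing to divert but keeps them in the comparison. The "threshold margin for non-inferiority will be 5"% on the risk-difference scale. The method is fixed: "We will construct Wald 95% confidence intervals (CIs) for a difference in diversion rates between the two arms". The decision is to "examine if the lower bound of the 95% CI is greater than the threshold margin".

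The outcome (Main outcome variables, Aim 2) is a composite of any one of three behaviours over 24 weeks: monitor adherence below 90%, self-reported selling, or a buprenorphine-negative urine while prescribed.

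The power analysis (D.10) gives two relevant sets of figures:

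- For Aim 1: "Engagement after passive referral may be as low as 0"%, and referral to methadone treatment has led to 9–16% engagement.
- For Aim 2: taking diversion to be 10–25% among 250 participants, the plan says "we will only have 80% power to declare that diversion rate in the O-BMT arm is non-inferior to the referral arm" at margins of 10–14%. The plan concedes that these exceed what would be tolerable.

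The 10–25% is not split by arm, and no referral-arm diversion rate is stated. The note to Table 3 switches to Fisher's exact test when referral engagement is near zero, but only for Aim 1. For H4 the plan names no alternative for sparse counts. The general promise to check test assumptions names no fallback.

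**The concern.** The Wald interval takes its variance from the observed proportions, so an arm with no events contributes no variance. When counts are small the interval is also symmetric around a difference whose distribution is skewed. Both push the upper limit down. For a harm such as diversion, non-inferiority depends on the upper limit of O-BMT minus referral, so the error favours declaring O-BMT no worse. H4 is the only hypothesis under the safety aim, and a pass would be reported as evidence that onsite prescribing does not raise diversion.

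Whether this matters depends on how low the referral rate is. The denominator includes people never prescribed, and the plan's own referral engagement scenarios are low, so a rate of a few percent or less is a realistic case to guard against.

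**Working it through.** **Inputs.** 250 randomised 1:1, so n = 125 per arm, because the primary analysis is intention to treat and includes those lost to follow-up; margin 5 points; two-sided 95% interval, so 2.5% on the deciding side; referral engagement 0%, 9% or 16%; diversion 10–25%.

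**The plan's Aim 2 figure.** With equal rates p in both arms, the margin giving 80% power is (z + 0.842) × √(2p(1−p)/125). The square root is 0.0379 at p = 10% and 0.0548 at p = 25%.

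- One-sided 5% (z = 1.645): 2.487 × 0.0379 = 9.4% and 2.487 × 0.0548 = 13.6%. Rounded up, this is the stated 10–14%.
- One-sided 2.5% (z = 1.960), which matches the planned interval: 10.6% and 15.3%.

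So the stated margins reproduce, but at a one-sided 5% level rather than the 2.5% that a 95% interval implies.

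**Implied referral-arm rate.** Engagement × assumed diversion among those engaged: 0% × any rate = 0%; 9% × 10% = 0.9%; 9% × 25% = 2.25%; 16% × 10% = 1.6%; 16% × 25% = 4.0%. The range is 0–4%, or 0 to 5 events in 125.

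**A case that can be checked by hand.** Wald upper limit = d + 1.96 × √(p1(1−p1)/n + p0(1−p0)/n). Take no events in the referral arm.

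- 2/125 v 0/125: 0.016 + 1.96 × √(0.016 × 0.984/125) = 0.016 + 0.022 = 3.8%, which passes.
- 3/125 v 0/125: 0.024 + 1.96 × √(0.024 × 0.976/125) = 5.1%, which fails.
- Newcombe for 2/125 v 0/125: the upper limit equals the Wilson upper limit for 2/125, 5.6%, which fails.

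If the true rates are 5% and 0%, Wald therefore passes whenever O-BMT has at most 2 events: P(X ≤ 2 | 125, 0.05) = 4.8%. Newcombe passes at no more than 1 event: 1.2%.

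**Exact error rates.** Binomial probabilities were summed over all pairs of counts, with the O-BMT rate equal to the referral rate plus 5 points. Non-inferiority is declared when the upper limit is below 5%.

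| Referral rate | Wald | Wald ÷ 2.5% | Newcombe |
|---|---|---|---|
| 0% | 4.8% | 1.9 | 1.2% |
| 0.5% | 5.7% | 2.3 | 1.9% |
| 0.9% | 5.5% | 2.2 | 1.9% |
| 1.6% | 4.9% | 1.9 | 2.0% |
| 2.25% | 4.3% | 1.7 | 2.0% |
| 4% | 3.3% | 1.3 | 2.3% |
| 8% | 2.7% | 1.1 | 2.3% |
| 10% | 2.7% | 1.1 | 2.4% |
| 25% | 2.6% | 1.0 | 2.6% |

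The score method gives nearly the same values as Newcombe. A simulation of 2,000,000 draws agrees with the Wald column at the rates tried (for example 4.8% at 0% and 3.3% at 4%).

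**Nature of the fault.** Two-sided Wald coverage is 94.2% at a referral rate of 0% and 93.2% at 1%, so the interval is not grossly short overall. The misses are lopsided: 4.8% and 5.4% on the upper side against 1.0% and 1.4% on the lower.

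**Other margins.** At the 10% and 14% margins, Wald gives 6.0% and 5.5% at a referral rate of 0%, and 4.2–4.3% at 1%. The fault is not specific to the 5-point margin.

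**Cost in power.** At 16% v 33% engagement and 10% diversion among those engaged, the true rates are 1.6% and 3.3%. The chance of declaring non-inferiority is 45% with Wald and 27% with Newcombe.

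**The case against.** The main objection is that the plan does not state a near-zero referral rate. Its 10–25% is given for the intention-to-treat comparison, and at those rates Wald is essentially nominal. The multiplier is also uncertain:

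- The 0% figure is for passive referral and the 9–16% for methadone referral. This control arm gets expedited appointments, reminders and repeat referral, in people selected for interest and willingness.
- Engagement is measured at day 30, whereas diversion accrues over 24 weeks, so more people may become at risk.
- The composite is broad. If, as an assumption, half of a 16% engaged share met it, the referral rate would be 8% and the Wald error 2.7%.

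All of this stands. A reader might infer that the plan expects almost no referral-arm diversion, or that the error rate is doubled in general. The documents support neither: a doubling applies only at rates of about 0–2%. A reader might also rerun the check at 100 per arm, from the 20% attrition allowance. That allowance belongs to the Aim 1 sample size, and the primary analysis keeps those lost to follow-up.

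It is also fair that these error rates apply at an excess of exactly 5 points. Crossing the plan's engagement scenarios with 10% and 25% diversion gives 18 cases, 11 with a true excess above 5 points. In 8 of those 11, Wald falsely passes less than 1% of the time.

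Finally, the rule as written compares the lower bound with the margin. For O-BMT minus referral against +5% that would show inferiority, so the orientation must be corrected first. Correcting it leaves the Wald fault in place.

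What the objection does not remove is that the referral rate cannot be known in advance, the low case follows from the plan's own scenarios, and a better interval costs nothing in data.

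**Conclusion.** The point holds conditionally. If referral-arm diversion is about 0–4%, the Wald interval gives a false non-inferiority rate of 3.3–5.7%, or 1.3 to 2.3 times nominal. At 8% or more, including the plan's stated 10–25%, the excess is negligible. The fault is mainly asymmetry, with the upper limit too low, rather than a badly short interval.

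This rests on 125 analysed per arm, a true excess of 5 points, a rule read as the upper limit of O-BMT minus referral falling below 5%, and, for the 0–4% range, an assumed 10–25% diversion among those engaged. It is worth correcting before analysis, but it ranks below the orientation of the decision rule. It does not show that a non-inferiority finding would be wrong.

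**What to change.** In the Analysis section, Aim 2 (H4), replace the Wald interval with a Miettinen-Nurminen (score) or Newcombe 95% interval for O-BMT minus referral. Choose one and name it. In the same edit, state that non-inferiority requires the upper limit to lie below the margin. Redo the Aim 2 power statement in D.10 with that interval at one-sided 2.5%, giving an assumed diversion rate for each arm.

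The change needs no extra participants or data, and standard software provides both intervals. Because missing categorical data are to be multiply imputed, the SAP should also say how the chosen interval is pooled across the 20 imputations. The real cost is power when events are few: the interval is wider and somewhat conservative (1.2–2.3% at referral rates of 0–4%), as in the fall from 45% to 27% shown above. At the plan's stated 10–25% the two approaches differ little.
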